Currently, PTLD is treated with either single agent rituximab or with rituximab containing chemotherapy. The overall response rate (ORR) to single-agent rituximab has ranged from 37% to 69% ⁶⁻¹¹. The first prospective phase II study by Choquet et al evaluated single-agent rituximab in 43 SOT-related PTLD recipients who failed tapering of immunosuppression ⁷. They demonstrated an ORR of 34%, event free survival (EFS) of 72%, and overall survival (OS) of 67% at 1 year. Complete response (CR) rate in this trial after 4 doses of rituximab was 28%. Rituximab was well tolerated with only 2 grade 3 or 4 events related to rituximab – hypertension and purpura with myalgia. Neutropenia was reported in two patients ⁷. Another prospective study evaluated the efficacy of extended use of rituximab in 38 patients with PTLD ¹¹. After the first course of rituximab, 34% had a CR, which was further augmented to 61% when partial responders were given 4 additional doses. One episode of grade 4 neutropenia was the only serious adverse event observed. Elstrom et al retrospectively reviewed 35 patients with PTLD treated with rituximab and showed an ORR of 68% and median OS of 31 months with rituximab ⁸.

Currently there is no approved therapy for PTLD. Although single agent rituximab is commonly used to treat B cell PTLD, the overall response rate is around 60% with approximately 30% of the subjects attaining a complete response. In a subset of patients' inadequate response necessitates addition of chemotherapy to improve response rate and outcomes. The morbidity and mortality with combination chemotherapy is reported to be high in this population ⁸. In one analysis 52% patients treated with chemotherapy required hospital admission for complications and treatment related mortality was 26% ⁸. Due to these reasons treatment with novel targeted agents needs to be explored to improve outcomes and to minimize toxicity.

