3.2 Number of Subjects

We plan to enroll 62 patients.

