8.0 Adverse Events and Potential Risks

8.1 Acalabrutinib

See Section 5.3.2 of the Investigator Brochure for further information. A summary is provided here. An aggregate safety analysis of acalabrutinib monotherapy was conducted and included data from 7 studies. This pooled data included 614 acalabrutinib-exposed subjects with a median exposure of 21.9 months. Almost all subjects (609 [99.2%]) had at least 1 AE, and about half (334 [54.4%]) had at least 1 Grade ≥ 3 AE. The most commonly reported AEs of any grade were headache (42.3%), diarrhea (40.4%), fatigue (24.6%), nausea (23.6%), contusion (23.5%), cough (22.1%), and upper respiratory tract infection (21.7). Atrial fibrillation of any grade was seen in

22 (3.6%) patient, grade 3 events were seen in 8 (1.3%) patients, and grade 4 or 5 events were seen in 0 patients. The most frequently reported Grade ≥ 3 AEs were neutropenia (10.4%), anemia (7.5%), pneumonia (6.5%), thrombocytopenia (3.7%), and hypertension (3.1%). Grade 5 AEs were reported for 27 (4.4%) patients with the most common severe AE being infection (2.1%).

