14.2 Rational for Sample Size

The null ORR of single agent Rituximab is 60% based on literature ⁶⁻¹¹. We expect the ORR (CR +PR) of combination regimen be at least 75%. Using one-sample exact binomial test, 62 patients will ensure a power of 80% at two-sided type I error rate of 10% to detect such a difference. The trial will be considered a success if 44 or more CRs/PRs are observed out of 62 patients.

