14.4 Toxicity Monitoring

Toxicity is defined as any grade 4 adverse event or treatment related death. We will do interim looks for toxicity after every 15 patients have been treated and assessed for toxicity. If the estimated toxicity rate is higher than 20%, we will pause the study and a comprehensive safety assessment will be performed.

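### Section 14.4 gives treatment-related deaths no pause criterion of their own, so its response to deaths depends on a grade 4 rate that the documents do not give

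*Combined protocol and SAP*

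**What the plan says.** Section 14.4 holds the plan's only numeric safety rule. It has three parts:

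- Event: "Toxicity is defined as any grade 4 adverse event or treatment related death".
- Timing: "We will do interim looks for toxicity after every 15 patients have been treated and assessed for toxicity". Section 3.2 sets the size ("We plan to enroll 62 patients"), so the looks fall at 15, 30, 45 and 60 patients.
- Action: "If the estimated toxicity rate is higher than 20%, we will pause the study and a comprehensive safety assessment will be performed".

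Section 14.4 gives no boundary table and no operating characteristics. Section 14.3 gives both for futility (Tables 5 and 6).

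Other sections deal with deaths without a numeric criterion. Section 8.3.2 makes death a serious adverse event. Section 8.5.1 requires investigators to report every such event to the lead site within 1 business day, and Section 8.7 requires all of them to go to the Data and Safety Toxicity Committee (DSTC). Section 8.8 refers to the institutional monitoring plan. Section 6.4 lets the sponsor suspend the study.

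Two figures give context. Section 1.1 says of chemotherapy: "In one analysis 52% patients treated with chemotherapy required hospital admission for complications and treatment related mortality was 26" percent. Section 8.1 says of acalabrutinib monotherapy: "Grade 5 AEs were reported for 27 (4.4%) patients", over a median exposure of 21.9 months.

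**The concern.** Under 14.4 a treatment-related death weighs the same as any grade 4 event, and the rate must be strictly above 20%. Part of the case for the combination is that it should spare patients the mortality seen with chemotherapy, so the monitoring rule ought to react to deaths at rates well below that level. Without a criterion for deaths, the formal rule can stay silent after several of them. Whether it fires also depends on how many unrelated grade 4 events happen to occur. And because looks come only every 15 patients, a cluster of deaths between looks prompts no formal check under 14.4.

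**Working it through.** **Inputs.** Looks at n = 15, 30, 45, 60 and a pause if x/n > 0.20 (14.4); N = 62 (3.2). The estimate is read as the raw proportion of patients with a toxicity, since no other estimator is named. The mortality rates are scenarios. The non-fatal grade 4 rates are assumptions, because the documents give no overall grade 4 rate.

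**Check against the plan's own figures.** Section 14.4 has none to reproduce, so the method was tried on the efficacy design. For 44 or more responses in 62, the exact upper tail is 0.049 at a response rate of 60% and 0.812 at 75%, in line with 14.2 (two-sided 10%, power 80%). The multi-look recursion used below, applied to the Table 5 boundaries, gives early stopping of 0.84 at 60% and 0.17 at 75%, as in Table 6.

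**Boundaries implied by 14.4.**

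| n | largest count without a pause | smallest count that pauses |
|---|---|---|
| 15 | 3 (20.0%) | 4 (26.7%) |
| 30 | 6 (20.0%) | 7 (23.3%) |
| 45 | 9 (20.0%) | 10 (22.2%) |
| 60 | 12 (20.0%) | 13 (21.7%) |

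**How likely is it that no other patient has a grade 4 event?** With rate g among the others, the chance is (1 − g)^12 beside 3 deaths in 15, and (1 − g)^48 beside 12 deaths in 60.

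| g (assumed) | 3 in 15 | 12 in 60 |
|---|---|---|
| 2% | 0.78 | 0.38 |
| 5% | 0.54 | 0.09 |
| 10% | 0.28 | 0.006 |
| 20% | 0.07 | <0.001 |

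The 12-in-60 path also needs at most 3, 6 and 9 events at the earlier looks. It is an extreme boundary case; 3 in 15 is the practical one.

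**Chance that the current rule pauses by n = 60.** At each look, add the next 15 patients' Binomial(15, p) count to the running total, remove the probability at or above 4, 7, 10 or 13, and sum what was removed. With mortality d and non-fatal grade 4 rate g among the rest, p = d + (1 − d)g. For example, d = 0.10 and g = 0.05 give p = 0.145; d = 0.10 and g = 0.10 give p = 0.19.

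| d | deaths alone (g = 0) | g = 5% | g = 10% |
|---|---|---|---|
| 5% | 0.006 | 0.065 | 0.26 |
| 10% | 0.071 | 0.26 | 0.55 |
| 15% | 0.285 | 0.56 | 0.80 |
| 20% | 0.612 | 0.83 | 0.94 |

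At d = 26%, the chemotherapy figure in Section 1.1, deaths alone give 0.574 at the first look and 0.895 by n = 60.

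**Illustrative separate rule.** Limits of 3, 4, 5 and 6 deaths within 15, 30, 45 and 60 patients, by the same recursion on deaths only: 0.006, 0.13, 0.63, 0.92 and 0.99 at d = 2%, 5%, 10%, 15% and 20%. Checking at each death gives the same totals. These figures do not depend on g.

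**The case against.** The strongest reply is that the composite is more sensitive than a count of deaths alone. Every grade 4 event of any cause counts, so 3 deaths plus one further patient with a grade 4 event is 4/15 = 26.7% and pauses. Section 8.1 reports grade 3 or higher events in 54.4% of monotherapy patients, so a cohort with no grade 4 event is doubtful. This stands: pooling adds triggers. A reader might infer that 3 deaths in 15, or 12 in 60, would leave the trial running whatever else happened; that holds only under the conditions above.

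A reader might also infer that the rule has almost no power against an unacceptable death rate. That fits rates up to about 10% when deaths are counted alone, but not 20% or 26%, where the pause probability is 61% and 90%. Nor is reporting to the DSTC optional: 8.5.1 and 8.7 make it mandatory, and only the decision to suspend under 6.4 is discretionary.

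The futility rule gives some indirect protection. Efficacy is analysed in all treated patients (14.5), so a death before the end-of-treatment scan would presumably count as a non-response. If 75% of survivors respond (an assumption), 20% early mortality lowers the response rate to 0.80 × 75% = 60%, for which Table 6 gives early stopping of 0.84. At 10% mortality the rate is 67.5% and early stopping about 0.51. But this rule targets efficacy and does not call for a safety review.

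Finally, no section states a tolerable treatment-related death rate. The 4.4% covers grade 5 events not stated to be treatment-related, on monotherapy; the 26% belongs to chemotherapy. Any particular limit is therefore a judgement. That argues for the sponsor choosing the limits, not for having none.

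**Conclusion.** The gap is real but moderate. Treatment-related deaths have no numeric criterion, the threshold must be exceeded rather than reached, and formal looks come only every 15 patients. At 10% treatment-related mortality the chance of a pause is 7%, 26% or 55% as the assumed non-fatal grade 4 rate goes from 0 to 5% to 10%. Detection of deaths thus rests on an unrelated rate, and a pause, when it comes, does not show whether deaths or reversible events caused it.

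The result assumes the raw proportion, patients as the unit, and independence between patients. The estimator matters at the margin: a posterior mean under a Beta(1,1) prior would be (3 + 1)/(15 + 2) = 23.5% at 3 in 15 and would pause, but 14.4 specifies no prior.

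A reader might rate this as something that must be corrected before the trial can proceed. The documents do not support that: there is no contradiction or arithmetic error, the primary analysis is unaffected, mandatory reporting is in place, and a discretionary halt remains possible. Nor do the documents say that this is the first use of the combination in transplant patients. It is an improvement to consider.

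**What to change.** Keep the pooled 20% rule. Add to 14.4 a separate rule that pauses the study for safety review when cumulative treatment-related deaths reach a stated limit, checked at each death rather than only at every fifteenth patient. The sponsor should state the treatment-related death rate it regards as tolerable, derive the limits from it, and report operating characteristics as Table 6 does for futility. The same edit can say that the estimated toxicity rate is the observed proportion of patients, if that is meant.

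The limits of 3 in 15, 4 in 30, 5 in 45 and 6 in 60 are an illustration of what such a rule can do, not a recommended standard.

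The cost is a few sentences and no new data. With the illustrative limits, the downside is about a 13% chance of an unnecessary pause, not a stop, if true treatment-related mortality is 5%, and about 9% if it is 4.4%.

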14.5 Analysis Populations

All efficacy and safety analysis will be performed using the treated population, which consists of all subjects who receive any amount of study treatment. The analysis of DOR will only include subjects who have achieved objective response and will be measured from the first observation of DOR until date of progressive disease.

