12.1 Definitions

12.1.1 Overall Response Rate

Overall response rate (ORR) is defined as all patients that achieve a CR or PR based on end of treatment scans, using the Lugano Criteria.

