12.1.4 Duration of Response

Duration of response (DOR) is only measured in responders. DOR is defined as the time from documented response (CR or PR) to the time of confirmed disease progression or death due to any cause, whichever occurs first. Subjects who are still alive and free from progression at the time of data cutoff date, lost to follow-up, have discontinued study, or have initiated other non-protocol anti-tumor therapy (NPT) will be censored at the last tumor assessment when subjects are progression-free.

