14.0 STATISTICAL CONSIDERATIONS

14.1 General Considerations

This is an open-label, single-arm, phase II trial of Rituximab in combination with Acalabrutinib treating newly diagnosed B cell post-transplant lymphoproliferative disorder. The primary objective is to assess the efficacy of the combination regimen. The primary endpoint is overall response rate (ORR) 8 weeks after treatment completion. Secondary endpoints include complete response rate (CRR), partial response rate (PRR), duration of response (DoR), overall survival (OS), progression-free survival (PFS), time to treatment failure (TTF) and toxicity profile.

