14.6 Missing Data Handling

No imputation of values for missing data will be performed except that missing or partial start and end dates for AEs and concomitant medication will be imputed according to prespecified, conservative imputation rules. Subjects lost to follow-up (or drop out) will be included in statistical analyses to the point of their last evaluation.

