14.7 Endpoint Data Analysis

Patient characteristics will be summarized using mean, SD, range, frequencies, and percentages where appropriate. ORR will be estimated along with 90% CIs, and compared against the null using exact binomial test. Logistic regression model will be used to identify factors associated with response status. Survival endpoints will be estimated using Kaplan-Meier method and compared using log-rank test. Cox proportional hazard model will be used to identify factors associated with survival endpoint. Other analyses will be carried out as appropriate.

REFERENCES

1. Opelz G, Henderson R. Incidence of non-hodgkin lymphoma in kidney and heart transplant recipients. *The Lancet*;342:1514-6.
2. Cockfield SM. Identifying the patient at risk for post-transplant lymphoproliferative disorder. *Transplant Infectious Disease* 2001;3:70-8.

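### Section 14.5 ends duration of response at progression and gives it a circular start, while Section 12.1.4 also counts death from any cause; no passage says which section governs

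*Combined protocol and SAP*

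**What the plan says.** Two current sections describe how DOR is measured.

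- **Section 12.1.4 (Duration of Response)**, under the definitions in Section 12.1, starts DOR at documented CR or PR and runs it "to the time of confirmed disease progression or death due to any cause, whichever occurs first". It also lists who is censored. The list opens with "Subjects who are still alive and free from progression at the time of data cutoff date" and goes on to patients lost to follow-up, off study, or started on other anti-tumor therapy, all censored at their last progression-free tumor assessment.
- **Section 14.5 (Analysis Populations)** restricts the DOR analysis to patients with an objective response, which agrees with 12.1.4. It then adds that DOR "will be measured from the first observation of DOR until date of progressive disease".

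Neither section refers to the other. Section 14.6 says only that "Subjects lost to follow-up (or drop out) will be included in statistical analyses to the point of their last evaluation". Section 14.7 says "Survival endpoints will be estimated using Kaplan-Meier method" and gives no event rule for DOR. Section 14.1 lists DOR among the secondary endpoints.

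**The concern.** The two sections disagree on the event. Under 12.1.4 a responder who dies without progression has a DOR event on the date of death. Under 14.5 as worded, that patient has none. The start in 14.5 cannot be used as written, because it names the endpoint as its own origin. Section 14.5 also omits the word confirmed before progression.

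If 14.5 is followed, nothing says how a death without progression enters the Kaplan-Meier estimate. The data-cutoff category in 12.1.4 is for patients still alive, and 14.6 deals with loss to follow-up and drop-out. The natural reading is to censor at death; the other is to keep the patient as never progressed. Both give a curve above the 12.1.4 curve, so the discrepancy runs in one direction, in favour of the regimen.

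Such deaths are plausible here. The patients are transplant recipients who may remain on immunosuppression (Section 6.1), and Sections 8.1.1.2 and 8.2.1.2 warn of fatal infections with both agents. What is at stake is the meaning and level of one secondary endpoint.

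**Working it through.** The plan states no DOR figure, so there is none to reproduce. The check compares the texts and then works one illustration.

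**Texts side by side**

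| Element | Section 12.1.4 | Section 14.5 |
|---|---|---|
| Set | responders | responders |
| Start | documented CR or PR | DOR itself (circular) |
| Event | confirmed progression, or death from any cause | progressive disease |
| Censoring | listed | none stated |
| Which section governs | not stated | not stated |

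**Illustration: inputs**

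- Responders: 44. This borrows the threshold in Section 14.2, "The trial will be considered a success if 44 or more CRs/PRs are observed out of 62 patients", as a convenient count. It is not a forecast.
- Progressions among them: 9 (assumed).
- Deaths without progression: 2 (assumed), with 0, 1 and 4 shown for range.
- No other censoring, all event times distinct, and DOR treated as one of the survival endpoints of Section 14.7 (assumed).
- The estimate is read after all of these events have occurred.

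**Under 12.1.4**, progressions and deaths are both events, so the estimate is the proportion with neither: (44 − 9 − 2)/44 = 33/44 = 75.0%.

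**Under 14.5 with deaths censored**, the product-limit estimate multiplies (1 − 1/n) over the 9 progressions, where n is the number at risk at each. It depends on when the deaths fall:

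- Both deaths before any progression: 42 are at risk at the first progression, and the product telescopes to 33/42 = 78.6%.
- Both deaths after every progression: 44 are at risk at the first, and the product telescopes to 35/44 = 79.5%.

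A death placed before a progression shrinks that risk set and lowers the factor, so these two orders are the extremes.

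**Under 14.5 with the deaths kept as never progressed**, the estimate is (44 − 9)/44 = 35/44 = 79.5%, the upper end of the same range.

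| Deaths without progression | 12.1.4 | 14.5 | Difference (points) |
|---|---|---|---|
| 0 | 35/44 = 79.5% | 35/44 = 79.5% | 0 |
| 1 | 34/44 = 77.3% | 34/43 to 35/44 = 79.1% to 79.5% | 1.8 to 2.3 |
| 2 | 33/44 = 75.0% | 33/42 to 35/44 = 78.6% to 79.5% | 3.6 to 4.5 |
| 4 | 31/44 = 70.5% | 31/40 to 35/44 = 77.5% to 79.5% | 7.0 to 9.1 |

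**Primary design.** The rule in 14.2 counts CRs and PRs. For 44 or more of 62, the exact one-sided error at 60% is 0.0492 and the power at 75% is 0.812, in line with the stated design. Neither figure uses DOR.

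**The case against.** The strongest reply is that 12.1.4 is the definition and 14.5 is not a rival to it. Section 12.1.4 sits under a heading for definitions and supplies start, event and censoring. Section 14.5 is about analysis populations, and its main job is to restrict DOR to responders. Its trailing clause cannot be run alone, so an analyst must go to 12.1.4 and will find death counted there. PFS in 12.1.5 also counts death from any cause. Much of this stands: a report that follows 14.5 alone is possible rather than likely. It does not remove the fault, because 14.5 is in the statistical chapter, says how DOR is to be measured, names a different event, and is not made subordinate to 12.1.4 anywhere.

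It is also fair to say that progression-only duration is a different quantity and not in itself a biased one. The difference above is relative to 12.1.4, and every rate behind it is assumed.

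Three stronger readings may tempt a reader, and the documents do not support them.

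- *The DOR result will be inflated.* This requires both that 14.5 be followed and that at least one responder die without progression.
- *The plan picks responders at end of treatment but times them from the interim scan.* Section 12.1.1 defines ORR as "all patients that achieve a CR or PR based on end of treatment scans", Section 12.0 also assesses response after cycle 1, and 12.1.4 does not name the scan. No passage prescribes that mixture.
- *The differing rules on follow-up of stable-disease patients distort DOR.* Section 11.1.2 differs here from Section 6.5 and calendar footnote h, and those passages must be reconciled. But patients with stable disease after cycle 1 leave treatment as non-responders and are not in the DOR set, so this is a separate matter.

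**Conclusion.** The inconsistency is real, and 14.5 is wrong as worded: its start is circular and it leaves out an event that 12.1.4 counts. If 14.5 is followed, DOR exceeds the 12.1.4 value whenever a responder dies without progression. In the illustration with 2 such deaths the excess is 3.6 to 4.5 points. It is zero if 12.1.4 is followed or if there are no such deaths. That size rests on assumed counts and no other censoring; only the direction follows from the definitions themselves. The matter is confined to a secondary endpoint with no decision rule attached, and the ORR test, sample size and futility rule do not depend on it. It should be corrected before analysis, so that the event is not chosen after the data are seen.

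**What to change.** In Section 14.5, keep the restriction to patients with an objective response and replace the rest of the sentence with:

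*DOR is measured from the first documented response (CR or PR) to the earlier of confirmed disease progression and death from any cause, with censoring as defined in Section 12.1.4.*

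This repairs the start, restores death as an event, and leaves one set of censoring rules. It needs no new data, visits or patients. The cost is one sentence and a possibly less favourable DOR estimate than a progression-only reading would give. It does not decide whether patients who responded only at the interim scan belong in the DOR set; that is a substantive choice for the sponsor.

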14.6 Missing Data Handling

No imputation of values for missing data will be performed except that missing or partial start and end dates for AEs and concomitant medication will be imputed according to prespecified, conservative imputation rules. Subjects lost to follow-up (or drop out) will be included in statistical analyses to the point of their last evaluation.

